Worldwide COPD and asthma are prevalent diseases causing death, health problems, impaired quality of life and high costs for individuals and society [1-4]. The common treatment goal of both these illnesses are to achieve quality of life and maintain symptom control with the lowest possible dose of control medication [5]. Pharmacological therapies for respiratory diseases are commonly delivered by inhalers allowing for lung deposition of the medication. Guidelines for chronic obstructive pulmonary diseases (COPD) [6] and asthma [7] address that patients should receive regular education and correction of inhalation technique [8]. Acceptable inhalation technique is an effective prevention of uncontrolled symptoms and exacerbations for asthma and COPD [9].

Therefore, education of inhalation technique is a prerequisite to ensure good treatment response. The education of inhalation technique is usually given by nurses, pharmacists or medical doctors and includes training and demonstration of inhaler use and correction of errors at clinical appointment, by observing if patient correctly can manage critical steps of getting the inhaler ready for inhalation by shaking the inhaler, remove the cap, execute the dose correctly and hold breath after inhalation.

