
Choose the most appropriate inhaler device for the patient before prescribing treatment. Consider the preferred medication, available devices, patient skills, environmental impact and costs.Ensure that patient have no physical or functional barriers that limit use of the inhaler.Avoid use of multiple different inhalers types where possible, to avoid confusion.
CHECK:

Check inhaler technique at every opportunityAsk the patient to show how they use their inhaler (don't ask if they know how to use it)Identify any errors using device specific checklist (Table 2).
CORRECT:

Show the patient how to use the inhaler correctly with a physical demonstrating, e.g. by using a placebo inhaler.Check technique again, paying attention to critical steps putting patient at risk not receiving inhaled medication. You may need to repeat this process 2-3 times within the same session for the patient to master the correct techniques [21].Identify any errors using a device-specific checklist (Table 2).Consider an alternative device only if patient cannot use the inhaler correctly after several training attempts.Re-check inhaler technique frequently. After initial training, errors often recur within 4-6 weeks [22].
CONFIRM:

Clinicians should be able to demonstrate correct technique for each of the inhalers they prescribe.Pharmacists and nurses can provide highly effective inhaler skills training [23, 24]

If the patient can't use the available device(s) correctly proper education, this could be related to factors of physical dexterity, coordination, inspiratory flow and cognitive status. Different inhaler types require different inhalation techniques, so it is preferable to avoid prescribing different types of inhalers for the same patient. Furthermore, incorrect inhaler technique increases risk of severe exacerbation of asthma or COPD. Additionally, Inspiratory flow rates can be assessed with the mechanical devices. These hand-held manual meters enables assessment of PIF, in some cases through adjustable resistance selected for a relevant inhalator (DPI or MDI) [14].

An educational and training device embedded in a patient smartphone app, shared with healthcare providers, offers novel and potentially cost-effective opportunities for healthcare providers to easily assess and monitor the performance of patients' inhalation techniques.

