11	For Handyhaler or similar, check powder drug rests in capsule, if necessary, inhale again	Breathed out and away from the mouthpiece of the inhaler

Each subject in both intervention and control arm will receive standard assessment and instruction on inhalation technique according to criteria in Table 2 at baseline visit. The study endpoints will be collected at the follow-up visit (6-12 weeks).

Randomisation and masking

Each of the 80 subjects is stratified to block of 4 numbers according daily used inhaler of (1) DPI, (2) MDI or (3) both MDI/DPI. Simple randomisation (1 to 1) will be applied in each block and at each study site. The randomisation will be blinded for the evaluator at 6-12 week visit, which practically means that not the same study personnel will do the baseline randomisation and the final 6-12 weeks assessment of inhalation technique.

Endpoints

Primary endpoint is number of subjects presenting successful inhalation techniques as defined by objective endpoints divided by:

- DPI: PIF \geq 30 L/Min, time to PIF <0.5 seconds measured with the investigational device.
- MDI: inspiration time (> 3 seconds) and PIF less than 60 L/Min measured with the investigational device.
- Together with subjective critical endpoints at 6–12-week follow-up visit, assessed by study personnel, Table 2.

Secondary endpoints:

- Feasibility and safety of using the investigational device for education and training of inhalation technique based on questionnaire and interviews from subjects and healthcare personnel, Appendix 3.

Study personnel will get access and be trained in methods and procedures for informed consent, randomisation, investigational device, data collection and documentation. The study endpoints will be documented in electronic Case Report Form (CRF) provided by Karolinska Institutet. Data analysis will start as soon as all 80 included subjects have completed or considered to be lost to follow-up at 6-12 week's visit by local investigator.

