This RCT with multiple investigational sites consists of both primary and secondary level of asthma and COPD care to enabling generalizability of the results and implementation of the investigational device in different healthcare settings. Each study site has one local PI who is responsible for implementing and carry through the investigation. The local study team consist of experienced medical doctors and respiratory nurses in the field, who will receive support, training, and coordination in study procedures from the [name]'s research group at KI. The KI research group will ensure the implementation and progress of the study follow the time plan, but also transparency, streamline the collaboration and find local solution that can prevent occurrence of problems. The study sites will be monitored by Karolinska Trial Alliance (KTA) to ensure compliance with study protocol, safety rules and securing the integrity of subjects. KTA will also train and educate study personnel in Good Clinical Practice (GCP).

Completion of study will be done after subjects have completed the 6-12 weeks follow-up visit, but not later than 12 weeks. Subjects who do not attend the follow-up visit within specified timepoint will be lost to follow-up, not replaced and withdrawn from the primary analysis. Information about feasibility and safety (secondary endpoints) will be collected by healthcare personnel at the

investigational sites after 12 weeks if the study subject has used the investigational device. The investigational device will be removed from the AsthmaTuner app after study completion by [name] research group at Karolinska Institutet. The stratified block randomisation 1:1 between intervention and control arm per study site will ensure the reliability and validity of study results by eliminating selection bias, balance confounding variables.

A.6.2 Investigational device and comparator

Investigational device:

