Subjects lost to follow-up will not be replaced but the decision will be documented in the medical record. Subjects who not attend the follow-up visit 12 weeks after the baseline visit will be categorised as lost to follow-up. They will be asked through email, phone or letter to send in the medical device to the study centre with envelope they received when they received the device at baseline visit. Study sites will be informed about which subjects were lost to follow-up.

Point of enrolment and randomisation

At least 80 subjects will be invited to participate in the investigation, through phone, digital meeting (Teams or Zoom or similar) or at physical at the baseline visit. The study personnel at investigational site will contact the study centre through phone to receive the randomisation assignment and study ID. The anticipated distribution is a minimum of 10 subjects per each participating investigational site.

Expected duration of each subject's participation is 6-12 weeks after enrolment to the investigation. The follow-up visit will be booked 6 weeks after study enrolment but no longer than 12 weeks. Subjects unable to attend the 6-12-week follow-up visit will be withdrawn from the primary analysis of study. The number of subjects required to be included in the investigation is estimated on background of power calculation (see section A7). The timeline is to enrol subject to the investigation during the fall of 2024 and spring of 2025. No additional care is required after the investigation beyond what was initially planned for each subject.

Target and vulnerable populations

The target population for the medical device are patient treated for asthma or COPD or any other disorder requiring treatment with DPI or MDI in primary or secondary care setting. However, neither patient with other diagnosis or children under the age of 16 years will not be included in the study. Although schoolchildren below the age of 16 are considered as target populations for the medical device, we consider we have sufficient data from this population from the pilot study (Appendix 4). Vulnerable, pregnant and breastfeeding population fulfilling the inclusion criteria are welcome to participate, no adverse effects or events are expected in this vulnerable population as longs they will be able to attend the follow-up visit.

A.6.4 Procedures

The subjects will undergo the following procedures as summarized in Table 3.

Procedures	Baseline visit	6–12-week follow-up visit

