The subjective assessment of inhalation will be conducted ‘blinded’ by study personnel. The assessment will be filmed through Teams or Zoom to facilitate standardised review and judgment of inhalation technique according to Table 2. The film is stored on local hard disk of the computer and will be deleted after the “blinded” assessment is done.

The objective assessment will be performed in both groups according to Figure 3 a-c. Data is stored in the AsthmaTuner cloud.

Compromising factors that might affect the outcomes are i.e. ongoing exacerbation (asthma or COPD), the follow-up visit can therefore be rescheduled within the time frame of 6-12 weeks in case of any medical condition is deemed to affect the study endpoints. The coordinating investigator will

take the decision to withdraw subject in case of any not resolved medical condition, not present at baseline visit, is judged to significantly affect inhalation technique or subject's safety at the follow-up visit.

A.6.5 Monitoring plan

Before the beginning of the investigation, the Sponsor will appoint an independent monitor at Karolinska Trial Alliance (KTA). Monitoring will be performed before, during the study and after the study is completed in accordance with the ISO 14155 GCP (Good Clinical Practice) standard. Study conductance, source data, device accountability, adherence to the study protocol, Good Clinical Practice, and regulatory requirements will be monitored.

Data to be monitored at site are e.g.

- Patient information and Informed Consent. That each patient included in the study has signed an Informed Consent and that no study procedures have begun before the date of the consent.
- That inclusion criteria are met for the included patients
- That all types of adverse events and serious adverse events, device related or not, as well as, those that might have led to SAE shall be reported, and even if those are listed as expected in this Clinical Investigation Plan.
- Check that all CRF data are entered
- Other CRF data will be source data verified against patient records according to a detailed Monitoring Plan (that will contain details regarding the overall monitoring) signed by the Sponsor prior to the start of the study. At least 10% of the patients will have data in the CRFs 100% source data verified.

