The monitor and possible authorities must be given direct access to source documents (original documents, data and records). Direct access includes permission to examine, analyse, verify and reproduce any record(s) and report(s) that are important to the evaluation of the clinical study. In order to be able to do that, a written consent from each patient should be obtained. Additionally, a secrecy agreement between the monitor and the person responsible for patient records at the study site will be signed.

A.7 Statistical considerations

The analytical approach of this RCT is intention-to-treat, analyzing the effect of the investigational device across all randomized subjects with assessed inhalation technique at the 6–12-week follow-up visit. Additionally, a per-protocol analysis will be conducted on subjects who performed an inhalation test on average more than once per week during the study period, to evaluate the efficacy of education and training on inhalation technique between the intervention and control groups.

The null hypothesis of this investigation is no difference in success rate of inhalation technique between subjects assigned to intervention or control group. If the number of patients with inhalation technique deemed for correction differ significantly between intervention and control group at 5% significance level, the null hypothesis will be rejected. Based on our cross-sectional pilot study, 50% of in 40 patients with asthma demonstrated successful inhalations technique (Appendix 3), assuming +25% absolute change of correct inhalation technique in the intervention group compared with control group including 20% drop out rate, enrolment of at least 80 patients will be sufficient to reach 80% power at 5% significance level.

Primary analysis: The success rate of subjects with correct inhalation technique according to objective and subjective critical endpoints at the 6-12 weeks follow-up visit. The effect of the medical device on rate of successful inhalation technique will be determined across randomisation groups with logistic regression analysis as risk ratio (RR) with 95% confidence interval. No interim analysis will be performed.

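### A.6.4 permits withdrawal of a randomised subject at follow-up because a new condition is judged to affect inhalation technique, the primary endpoint, and does not require that judgement to be masked or made before technique is seen

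*Protocol*

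**What the plan says.** In A.6.4, under the 6-12 week follow-up visit, the protocol names an ongoing exacerbation of asthma or COPD as an example of something that could compromise the outcomes. It says that "the follow-up visit can therefore be rescheduled within the time frame of 6-12 weeks" when a medical condition is thought to affect the endpoints. It then gives the coordinating investigator the decision to "withdraw subject in case of any not resolved medical condition, not present at baseline visit, is judged to significantly affect inhalation technique". Subject safety is a second ground in the same sentence and is not at issue here.

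Three other parts of the protocol bear on this rule.

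- **Analysis set.** A.7 calls the approach intention-to-treat but applies it to "all randomized subjects with assessed inhalation technique at the" follow-up visit. In A.6.1, subjects who do not attend in the window "will be lost to follow-up, not replaced and withdrawn from the primary analysis". The one sensitivity analysis in A.7 changes the endpoint definition (all subjective criteria rather than the critical ones), not the handling of withdrawn subjects.
- **Masking.** A.6.1 states: "The randomisation will be blinded for the evaluator at 6-12 week visit". A.16 says more generally that physicians and investigators are not to be told the allocation. In A.6.3, the study coordinator and a medical doctor decide whether a subject should stop using the device, and site personnel "contact the study centre through phone to receive the randomisation assignment and study ID".
- **Technique and exacerbation.** A.1.1 states: "Acceptable inhalation technique is an effective prevention of uncontrolled symptoms and exacerbations for asthma and COPD". A.2.I states that "incorrect inhaler technique increases risk of severe exacerbation of asthma or COPD". A.6.3 adds that a severe exacerbation, or the severity of obstruction, affects technique.

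**The concern.** The ground for withdrawal is an expected effect on the variable that the trial measures. Subjects removed on this ground are mostly those expected to fail, and they are removed after randomisation by judgement, with no objective criterion. This is separate from loss to follow-up, because the wording covers a subject who is present and could be tested.

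The comparison is biased if such removals differ by arm, which can happen in two ways. First, on the protocol's own reasoning, better technique prevents exacerbations. If the app works, the trigger may be commoner among controls; removing those subjects raises the control success rate and hides part of a real effect. Second, nothing in A.6.4 prevents the judgement from being influenced by knowledge of arm or by having watched the subject inhale; that could move the estimate either way. Masking would deal with the second route but not the first.

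The protocol describes the trial as confirmatory and as the basis for a superiority claim. With 80 subjects, a few such decisions are enough to matter.

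**Working it through.** **Step 1: can the rule remove a subject from the primary analysis?** A.6.4 does not say whether the decision comes before or after the technique assessment.

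- Withdrawn before assessment: there is no assessed technique, so the subject falls outside the A.7 set.
- Withdrawn after assessment: the subject still meets the A.7 definition but has been withdrawn. The protocol does not say which prevails.

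Explicit removal from the primary analysis is written only for non-attenders (A.6.1, A.6.3). For withdrawn subjects it is inferred from A.7.

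**Step 2: is the decision masked?** A.16 would keep allocation from investigators, and the coordinating investigator is one. A.6.1 specifically blinds only the follow-up evaluator. A.6.3 has the study coordinator and a doctor decide about stopping the device, which implies knowing who has it, and has the study centre issue assignments by phone. These statements fit poorly together, and A.6.4 does not settle the matter for this decision.

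**Step 3: size, under the plan's own rates.** The protocol gives no expected number of these withdrawals, so there is no plan figure to reproduce and the number removed is an assumption. Inputs: success 50% versus 75%, 80 subjects, 1:1 allocation and 20% dropout (A.1.5, A.6.1, A.7). Evaluable per arm = 80 × 0.8 / 2 = 32.

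- No removal: 16/32 = 50.0% versus 24/32 = 75.0%; difference 25.0 points, RR 0.750/0.500 = 1.50.
- Three failing controls removed: 16/29 = 55.2%; difference 75.0 − 55.2 = 19.8 points, RR 0.750/0.552 = 1.36.
- Three failing app subjects removed: 24/29 = 82.8%; difference 82.8 − 50.0 = 32.8 points, RR 24/29 ÷ 16/32 = 1.66.
- Three failures removed from each arm: 16/29 versus 24/29; difference 8/29 = 27.6 points, RR 24/16 = 1.50.

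The base of 32 is already net of the dropout allowance. Starting instead from all 40 per arm (20/40 versus 30/40), three one-sided removals give 75.0 − 20/37 (54.1%) = 20.9 points, or 30/37 (81.1%) − 50.0 = 31.1 points. The picture is the same.

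**Step 4: size when there is no true effect.** Assume 50% success in both arms, 32 assessed per arm, a two-sided 5% pooled z-test with exact binomial enumeration, and k failures removed from the app arm only.

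- k = 0: nominal app rate 16/32 = 50.0%; chance of a false finding in favour of the app 3.0%.
- k = 2: 16/30 = 53.3%; 5.2%.
- k = 4: 16/28 = 57.1%; 9.2%.
- k = 6: 16/26 = 61.5%; 16.0%.

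With 40 per arm, the chances for k = 0, 2, 4 and 6 are 2.8%, 4.7%, 7.8% and 12.6%.

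**The case against.** The rule is narrow. It covers only a condition that is new since baseline, unresolved, and judged to affect technique significantly, and the visit may be rescheduled first. It applies to both arms. Measuring learned technique outside acute illness is a defensible aim, and the exclusion criteria already bar conditions that affect the ability to inhale. If exacerbations are commoner in controls, the bias runs against the app, which is conservative for a superiority claim.

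Much of this stands. The group affected is probably small, and the direction of bias is not known. But a rule worded alike for both arms does not give equal removals when its trigger can depend on treatment. Rescheduling is optional, rests on a similar judgement, and has no masking requirement either. The alternative aim can be met by a sensitivity analysis without making removal the primary rule. A statistical analysis plan could set a rule for missing outcomes, but it could not recover a technique that was never measured.

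A reader might go further in four ways that the protocol does not support.

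- That the decision is unmasked. A.16 says investigators are not to be told the allocation. The most that can be said is that A.6.4 does not require masking and other sections sit uneasily with A.16.
- That staff who know the assignment report the condition. The protocol does not say who reports it, and A.6.1 separates the staff who randomise from those who assess.
- That the protocol expressly drops these subjects from the primary analysis. That is an inference from A.7.
- That three or more failures would be lost from one arm. That is a constructed case.

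**Conclusion.** The concern holds in this limited form. A.6.4 permits removal after randomisation on a judgement tied to the primary endpoint, without requiring the decision to be masked or to precede the assessment. Through A.7, a subject withdrawn before assessment is lost from an analysis called intention-to-treat. Because the protocol links technique and exacerbation in both directions, arm-dependent removal is plausible even with perfect masking.

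The size cannot be estimated from the protocol. If three failures were removed from one arm only, the planned 25-point difference would shift by about −5 or +8 points. If four were removed from the app arm only, with no true effect, the chance of a false finding for the app would about triple. These results rest on the assumed numbers, on all those removed being failures, and on removal from a single arm. Removal from both arms equally would leave the RR at 1.50 and change the difference by under 3 points.

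**What to change.** In A.6.4, remove the expected effect on inhalation technique as a ground for withdrawal from the primary analysis, and state the following:

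- A subject who attends in the window and is assessed is scored as observed and kept in the primary analysis, with the condition recorded in the CRF.
- Excluding such subjects is a sensitivity analysis.
- Any decision to reschedule because a condition may affect the endpoints is made and recorded before technique is seen, without knowledge of arm.
- Withdrawals are reported by arm with reasons.

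The safety ground and its handling stay unchanged. Separately, reconcile A.6.1, A.6.3 and A.16 on who may know the allocation.

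The cost is a short change to A.6.4, the masking clarification and one CRF field. The downside is that a few outcomes measured during an acute condition add some noise.

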Procedures: At baseline, a trained respiratory nurse will subjectively assess and train each patient's inhalation technique according to defined criteria of device handling (standard education). The AsthmaTuner app is downloaded to a smartphone or tablet computer (Ipad) that is wirelessly (Bluetooth) connected to a home spirometer. In this study the Bluetooth spirometer AsthmaTuner from MIR will be used. Education and training of inhalation technique will include measurement of inhalation flow with an adjustable resistance mounted on the spirometer, Airflow Trainer (MIR). The app gives instruction to set the resistance, so it corresponds to the selected inhaler. Questionnaires and interviews will collect information about the feasibility, safety and experienced usability of the investigational device.

Analysis: The rate of subjects with successful inhalation technique at 6–12-week visit determined by fulfilling objective and subjective critical endpoints in intention-to-treat approach. The effect of using the inhalation app-module will be analysed with logistic regression analysis across randomisation groups. The secondary analysis of feasibility and the experienced benefit of using the inhalation app-module in clinical practice and for patient's education and training of inhalation technique is estimated on a Likert scale from 1 (not at all) to 5 (strongly agree) and presented as mean and median scores.

A.2 Identification and description of the investigational device

A.2.A Description of the investigational device

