A.6 Design of the clinical investigation

A.6.1 General

This confirmatory multicentre two-armed stratified randomised controlled blinded study analysing the effect of app-based education and training of inhalation technique compared with control group on subjective critical and objective endpoints of inhalation technique at 6-12 weeks follow-up visit. The study approach is intention to treat, including 80 subjects with daily therapy of DPI and/or MDI for asthma and/or COPD, Figure 2.

[figure not shown]

Figure 1 Two-armed, parallel-designed, individual single-blinded stratified randomised controlled trial.

The subjects will be randomly assigned to one of the following two arms (1:1):

1. Standard assessment and correction together with app-based education and training at baseline visit and at least every week or whenever needed during the following study period of 6-12 weeks.
2. Standard assessment and instructions on inhalation technique at baseline visit according to Table 2.

Table 2. Subjective assessment of handling and inhalation techniques, adopted from Aksu F. et al. [8]. If all criteria are not deemed to correction per inhaler, including objective endpoints defines primary endpoint of subject with successful inhalation technique.

	DPI	MDI
1	Shook inhaler (critical for Easyhaler)	Shook the inhaler (critical for suspension)
2	Removed the cap of the inhaler correctly (critical)	Removed the cap of the inhaler correctly (critical)
3	Actuated one dose / loaded capsule correctly (critical)	Breathed out before slow inhalation
4	Inhaler kept in upright position (critical for some inhalers)	Breathed out and away from the mouthpiece of the inhaler
5	Breathed out and away from the mouthpiece of the inhaler	Placed the inhaler mouthpiece correctly in mouth
6	Inhaler correctly placed in mouth. Inhaled with lips sealed around the mouthpiece (critical)	Inhalation slow before or immediately when dose fired (critical)
7	Inhaled forcefully through the mouth after firing dose (critical)	Inhaled through the mouth after dose fired (critical)
8	Inhaled without interruption (critical)	Inhaler was correctly placed in mouth during the entire inhalation (critical)
9	Breath-holding more than 5 seconds after inhalation	Inhaled without interruption (critical)
10	Breathed out and away from the mouthpiece of the inhaler	Breath-holding more than 5 seconds after inhalation

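### The primary analysis is called intention-to-treat but is an available-case analysis, and no effect analysis stated in the protocol keeps all randomised subjects

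*Protocol*

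**What the plan says.** The intention-to-treat label appears in three places.

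- A.1.5 (synopsis, Analysis): the success rate is "determined by fulfilling objective and subjective critical endpoints in intention-to-treat approach".
- A.6.1: "The study approach is intention to treat". The same sentence gives the number of subjects as 80.
- A.7: "The analytical approach of this RCT is intention-to-treat, analyzing the effect of the investigational device across all randomized subjects with assessed inhalation technique". Here the label and its restriction stand in one sentence.

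The exclusion is also fixed in two other places.

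- A.6.1: "Subjects who do not attend the follow-up visit within specified timepoint will be lost to follow-up, not replaced and withdrawn from the primary analysis".
- A.6.3 (Point of enrolment and randomisation): "Subjects unable to attend the 6-12-week follow-up visit will be withdrawn from the primary analysis of study".

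A.7 names two further analyses of the effect. One is narrower: "a per-protocol analysis will be conducted on subjects who performed an inhalation test on average more than once per week during the study period". The other, called the sensitivity analysis, only widens the set of subjective criteria that count towards success. The sample size paragraph of A.7 anticipates the loss: "assuming +25% absolute change of correct inhalation technique in the intervention group compared with control group including 20% drop out rate".

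A.6.4 also lets the coordinating investigator withdraw a subject at follow-up for a new, unresolved medical condition judged to affect inhalation technique or safety. It does not say whether such a subject stays in the analysis.

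**The concern.** Intention-to-treat has two parts: subjects are compared in the arm to which they were randomised, and everyone randomised is counted. The protocol keeps the first part and removes the second. A result reported under this label would claim a protection that the analysis does not have.

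This matters because A.6.1 calls the trial confirmatory and A.5 ties it to a superiority claim. Subjects cannot be blinded (A.8), and only the app arm is asked to train repeatedly at home, so loss could differ between arms and could relate to technique. If it did, the available-case comparison would be biased, and no effect analysis stated in the protocol would reveal how far the conclusion depends on the subjects left out.

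**Working it through.** **1. Who is analysed.** A.6.1, A.6.3 and A.7 agree: randomised subjects with an assessed outcome at 6-12 weeks, by assigned arm. The per-protocol set is a subset chosen by device use. The sensitivity analysis changes the endpoint, not the set. The descriptive table reports the number randomised but estimates no effect. So no stated effect analysis contains all randomised subjects.

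**2. How many are left out.** From A.7: 80 enrolled, 20% dropout. 80 × 0.20 = 16 excluded, 64 analysed. Whether 80 is enough is a separate question and is not used here.

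**3. Inputs for an illustration.** Success rates of 75% and 50% (A.1.5) and 1:1 allocation (A.6.1) are the protocol's. Assumed: 40 randomised and 8 missing per arm, and a two-sided uncorrected chi-square test.

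**4. Formulas.**
- z = (p1 − p2) / √[p̄(1 − p̄)(1/n1 + 1/n2)]
- SE of log RR = √(1/a − 1/n1 + 1/b − 1/n2), with a and b the successes per arm

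**5. Available cases, 24/32 versus 16/32.**
- p̄ = 40/64 = 0.625; z = 0.25/√(0.625 × 0.375 × 2/32) = 0.25/0.1210 = 2.07; p = 0.039
- RR = 1.50; SE = √(1/24 − 1/32 + 1/16 − 1/32) = 0.204; 95% CI 1.005 to 2.24

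**6. All randomised, missing counted as failure, 24/40 versus 16/40.**
- p̄ = 40/80 = 0.50; z = 0.20/√(0.25 × 2/40) = 0.20/0.1118 = 1.79; p = 0.074
- RR = 1.50; SE = √(1/24 − 1/40 + 1/16 − 1/40) = 0.233; 95% CI 0.95 to 2.37

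**7. Range over other assumptions about the 8 missing per arm.**

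| Missing subjects | App | Control | Difference | RR (95% CI) | Chi-square p |
|---|---|---|---|---|---|
| Same rates as those observed, counted as observed | 30/40 | 20/40 | 25 points | 1.50 (1.05 to 2.15) | 0.021 |
| Both arms at the control rate | 28/40 | 20/40 | 20 points | 1.40 (0.97 to 2.03) | 0.068 |
| App all fail, control all succeed | 24/40 | 24/40 | 0 | 1.00 | 1.00 |
| App all succeed, control all fail | 32/40 | 16/40 | 40 points | 2.00 | <0.001 |

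The first row treats filled-in outcomes as real observations, so its precision is overstated.

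**8. Tipping grid.** Let x and y (0 to 8) be the successes among the missing in the app and control arms. By chi-square, p < 0.05 exactly when x is at least y + 1. On the risk-ratio scale (Wald test of log RR) the same boundary holds except in two cells, 25/40 versus 16/40 and 26/40 versus 17/40, both p = 0.051.

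**9. When bias would arise.** Suppose there is no true effect (50% success in both arms), 20% loss per arm and random control loss. If app-arm failures drop out k times as often as successes, the success dropout is s = 0.4/(1 + k) and the observed app success rate is 0.5(1 − s)/0.8. Exact rejection rates at 32 per arm:
- random loss: 6.0%
- k = 2 (observed rate 0.542): 7.4%
- k = 3 (0.5625): 9.2%
- every app-arm loss a failure (0.625): 18.9%

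The mirror patterns give the same rates with the bias against the app. If the extreme pattern occurs in both arms, the rate is 5.4%.

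**The case against.** The protocol is open about its analysis set. The A.7 sentence that uses the label also states the restriction, and A.6.1 and A.6.3 repeat it plainly, so a careful reader is not misled about who is analysed. Missing-data methods commonly sit in an SAP, which is not shown, and the protocol does not bar supportive analyses. This stands as a limit on the point: absent imputation or tipping-point detail is not the finding. What remains is that the protocol itself fixes the exclusion under a label that says otherwise.

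The figures also deserve restraint. Under equal loss with missing counted as failure the protocol's effect measure does not move (RR 1.50 in both analyses); only its precision and the p-value change. A result at p=0.039 is fragile anyway in 64 subjects: Fisher's exact test on the same available cases gives p=0.070. Even random loss gives a 6.0% rejection rate in step 9, so twofold or threefold selective dropout adds only about 1 to 3 points.

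A reader might infer that the planned analysis is biased towards the app, or that the superiority claim would be a false positive. The documents do not support that. They give one overall dropout figure, no split by arm, and nothing on outcomes among those lost. Loss unrelated to outcome would not bias the estimate, and selective loss could favour either arm.

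**Conclusion.** The label is wrong as written. The primary set is all randomised subjects with an assessed outcome, analysed as assigned, and about 16 of 80 would fall outside it at the stated dropout. That part rests on the text alone.

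The effect on the conclusion is conditional. With 8 missing per arm, the planned result can lie on either side of p=0.05, and the difference can range from 0 to 40 points, according to what is assumed about the missing. The equal split and the outcomes among the missing are assumptions, and some of this sensitivity belongs to the sample size rather than to the exclusion. Bias is possible but not demonstrated. The point should be fixed because the remedy is cheap and would show whether the superiority conclusion depends on the excluded subjects.

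**What to change.** - **Relabel.** In A.1.5, A.6.1, A.6.3 and A.7, describe the primary set as all randomised subjects with an assessed outcome, analysed in their assigned arm (available-case or modified intention-to-treat).
- **Add one prespecified sensitivity analysis** of all 80 randomised subjects in their assigned arm, with missing outcomes counted as failure in both arms.
- **Add a tipping-point grid** over the possible numbers of successes among the missing in each arm, reported on the protocol's risk-ratio scale. The detail can sit in the SAP.
- **Clarify A.6.4 withdrawals.** In that sensitivity analysis, a subject withdrawn under A.6.4 counts as randomised with a missing outcome. The clinical decision to withdraw is unchanged.

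The cost is wording and a little more analysis work. No visits or data are added, because A.6.1 already requires every subject to be classified before analysis: "Data analysis will start as soon as all 80 included subjects have completed or considered to be lost to follow-up". The downside is that the all-randomised estimate may be smaller or less precise than the available-case one.
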